6.0 Procedures Involved*

- 6.1 An individual's participation will occur during a lumbar medial branch block procedure. All subjects will have qualified for a lumbar medial branch block due to axial low back pain with lumbar spondylosis as the primary diagnosis. All subjects would have received lumbar medial branch blocks during their normal clinical course whether or not they choose to participate in this study
- 6.2 This study will focus solely on skin wheal creation and resulting skin anesthesia with lidocaine 1% and bacteriostatic saline. The lumbar medial branch block procedure typically requires two or more skin wheal injections prior to placement of the spinal needle that ultimately delivers the block. Subjects will serve as their own control. The first two skin wheals will be utilized for the study and the medications will be randomized with both the subject and investigator blinded to the medication used for each one. The first two skin wheals and placement of the first two spinal needles through these skin wheals will be performed by the principal investigator to promote consistency.
- 6.3 Using a standardized script, the participant will be informed that the medication will be administered. The skin wheal will be created by injecting the medication intra-dermally with a 26 gauge needle. The patient will be asked to rate on the numerical rating scale (NRS) the pain experienced with creation of the skin wheal. This process will then be repeated with the second skin wheal. Next, the first needle for the block will be inserted through the first skin wheal. The patient will again be asked to rate, on the NRS, the pain of needle insertion. For this procedure, a 22 gauge Quincke spinal needle will be used with a length of either 3.5 or 5 inches. This process will again be repeated by inserting the second needle through the second skin wheal.
- 6.4 At this point, the individual's participation in the research study is complete and the lumbar medial branch block will be continued as usual with any subsequent skin wheals created with 1% lidocaine plain (standard of care, not study related). The remainder of the medial branch block (after the conclusion of the individual's participation in the study) may be performed by the pain fellow or the principal investigator (attending).

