- 6.5 Basic demographics (age, gender) and baseline pain score will be collected directly from the participant by the investigator before the intervention. During and after the intervention, the levels (L2, L3, L4, etc) and laterality injected and pain scores from the intervention will be collected directly from the subject by the investigator. No identifiable PHI will be collected or stored.

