16.0 Potential Benefits to Participants*

16.1 A potential benefit includes less pain with injection of BNS; however, the magnitude of this benefit is low since only one skin wheal will be created with BNS. The rest will be created with 1% lidocaine plain.

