17.0 Data Management* and Confidentiality

17.1 Data will be analyzed using SAS 9.4 (Cary, NC) by the Anesthesiology Department's Biostatistician. For the first hypothesis, a General Linear Model will be applied, which is equivalent to a modified matched-pairs t-test, but allows for inclusion of potential confounders, such as the injection order. If assumptions of the General Linear Model are not met, e.g. the data are too leptokurtic or too positively skewed, then another statistical test such as Ordinal Logistic Regression will be used instead. For the second hypothesis, a non-inferiority test will be conducted, calculating delta as the maximum value for the 90% confidence interval, with an effect size of 0.24, an alpha set at 0.1, and a standard deviation of the difference determined from the sample data.

17.2 Power analysis was conducted with G*Power 3.1.9.4 (Düsseldorf, Germany). [20] A two-tailed a priori difference between two dependent means (matched pairs) was conducted. Alpha (Type I error) was set at 0.05 and power was set at 0.80. An effect size was set at 0.46, which is the mean effect size of a meta-analysis, [15] and is lower than the effect size of 0.52 calculated for a similar study. [11] This yielded a minimum required sample size of N=40.

17.3 Guidelines provided by the Grady/Emory Data and Safety Monitoring Board will be followed for this study data. Envelopes with random assignment of subjects to treatment arms will be in a locked filing folder and stored at the Grady Pain clinic office. No names, MRNs, or other personal identifiers will be used for the subjects - they will be given a random number identifier. Data results of subject's VAS scores will be immediately loaded to an encrypted and password protected Excel file and/or RedCap. The principal and secondary investigators will have access to the locked office/filing folder. If any reportable events are identified, they will be reported to the IRB as required by regulations. All study records will be reviewed at least annually.

17.4 Data results of subject's NRS scores will be immediately loaded to an encrypted and password protected Excel file and/or RedCap. The data will include the randomly assigned number identifier of the subject and the result of their NRS score. Data will be stored for 3 years. Only [name]

PROTOCOL TITLE: Bacteriostatic Normal Saline versus lidocaine for intradermal anesthesia during lumbar medial branch block.

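### The two drug orders are neither named nor balanced, and 17.3 speaks of treatment arms in a within-patient design; randomise sequence 20:20 and require an order term for both hypotheses

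*Combined protocol and SAP*

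**What the plan says.** **Design.** Section 6.2 states "Subjects will serve as their own control", and 16.1 confirms that "only one skin wheal will be created with BNS". Both treatments are therefore given to every patient.

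**Allocation.** Section 6.2 says "the medications will be randomized with both the subject and investigator blinded to the medication used for each one". Section 17.3 describes the mechanism as "Envelopes with random assignment of subjects to treatment arms will be in a locked filing folder". Neither place names the two possible sequences, a ratio, a block size or any counterbalancing.

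**Order of events.** Under 6.3 both wheals are made and scored first. "Next, the first needle for the block will be inserted through the first skin wheal", and the step is repeated by "inserting the second needle through the second skin wheal". The drug in the first wheal is thus also the drug under the first needle.

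**Site.** Section 6.5 records "the levels (L2, L3, L4, etc) and laterality injected", but no rule says which site is injected first.

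**Analysis.** For Hypothesis 1, 17.1 plans a general linear model, equivalent to a modified paired t-test, that can take in confounders; injection order is its example. For Hypothesis 2 it gives a 90% confidence interval, an effect size of 0.24, alpha of 0.1 and the SD of the difference from the sample. It mentions no order term there.

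**The concern.** In a two-position within-patient trial, a second painful stimulus may be scored differently from the first. If more patients receive BNS first than second, part of that difference is counted as a drug effect. Here a single draw per patient sets the position of the drug for the wheal score (Hypothesis 1) and for the needle score (Hypothesis 2), so one uneven split reaches both comparisons.

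The wording of 17.3 describes a parallel-group allocation. Taken literally it gives the person preparing the envelopes no sequence to write in them and no target of 20 per sequence. The plan itself names injection order as a possible confounder, but leaves adjustment optional for one hypothesis and unmentioned for the other. Hypothesis 2 is the more exposed, because a small shift is large beside 0.24 SD.

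**Working it through.** **Inputs from the protocol.** N = 40, two-sided alpha 0.05, power 0.80 and effect size 0.46 (17.2); 0.24, 90% interval and alpha 0.1 for Hypothesis 2 (17.1).

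**Assumptions, not in the protocol.**
- Order is drawn by simple randomisation.
- The order effect π (first-position minus second-position score) is 0.25, 0.5 or 1.0 SD of the paired difference within a sequence.
- Hypothesis 2 uses a margin of 0.24 SD and succeeds if the upper 90% limit lies below it, a one-sided 5% test.

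**1. The plan's own figure.** A paired t-test at effect size 0.46 has power 0.810 with N = 40 and 0.799 with N = 39. The stated 40 is reproduced.

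**2. Chance of an uneven split.** With X ~ Binomial(40, 0.5), exactly 20:20 has probability 0.125. A split of 24:16 or worse has 2·P(X ≤ 16) = 0.268; 26:14 or worse, 0.081.

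**3. Shift without an order term.** Let D be BNS minus lidocaine, with true mean τ. Patients given BNS first have mean τ + π, the others τ − π. With n1 and n2 patients, the mean of D is τ + π(n1 − n2)/40. At 24:16 the shift is π × 8/40 = 0.2π.

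| π (SD) | Shift at 24:16 (SD) | Share of 0.46 | Share of 0.24 |
|---|---|---|---|
| 0.25 | 0.05 | 11% | 21% |
| 0.5 | 0.10 | 22% | 42% |
| 1.0 | 0.20 | 43% | 83% |

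The standard error of the mean difference is 1/√40 = 0.158 SD.

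**4. Hypothesis 2, unadjusted, 24:16 favouring BNS, true difference at the margin.** The unmodelled order effect also widens the observed SD to √(1 + π²(1 − 0.2²)). The t quantile (39 df) is 1.685. Non-inferiority is declared falsely with probability about Φ(−[1.685 × SD × 0.158 − 0.2π]/0.158).
- π = 0.25: SD 1.030, Φ(−1.42) = 0.078
- π = 0.5: SD 1.114, Φ(−1.24) = 0.107
- π = 1.0: SD 1.400, Φ(−1.09) = 0.137

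Simulation, which does not use the normal approximation, gives about 8%, 11% and 14%. At 26:14 it gives 11%, 19% and 34%. At 20:20 the rate does not exceed the nominal 5%.

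**5. Hypothesis 1, unadjusted.** At 26:14 simulated two-sided type I error is about 0.07, 0.11 and 0.19 for the three order effects. Averaged over all splits from simple randomisation it is about 0.05.

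**6. With an order term.** Effective N is 4·n1·n2/40, with 38 df. Power at 0.46 is 0.809 (20:20), 0.793 (24:16), 0.772 (26:14) and 0.738 (28:12), averaging 0.799 over simple randomisation. Type I error is 0.05 at any split.

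**7. Balance without an order term.** At 20:20 the mean shift is zero, but the order effect stays in the error variance. At π = 0.5 SD, unadjusted power is about 0.74, against 0.81 with the term.

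**The case against.** The best defence is that 6.2 already randomises the medications across the two wheals. Random order is balanced in expectation, and type I error averaged over simple randomisation stays near 0.05. For Hypothesis 1, 17.1 offers an order term that removes the shift at any split, and blocking then gains only about one point of power on average (0.799 to 0.809). All of this stands. A reader might infer from 17.3 that order is not randomised, or that the drug comparison is biased; the protocol supports neither. Sections 6.2, 16.1 and the matched-pairs calculation in 17.2 make the within-patient design clear enough that conduct is unlikely to go astray, and the arms may simply mean sequences.

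The size also rests on assumptions. The protocol gives no order effect and no randomisation method, so a simple list cannot be taken as fact. Some 73% of simple draws are closer than 24:16, and an imbalance is as likely to favour lidocaine as BNS.

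What the defence does not meet is that the Hypothesis 1 term is optional, Hypothesis 2 has none, and a single trial is analysed at the split it happens to draw.

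**Conclusion.** The concern holds as a minor one. The allocation wording does not fit the design, the two sequences are neither named nor balanced, and adjustment for order is not secured. The consequence is conditional on the realised split: under simple randomisation there is a 27% chance of 24:16 or worse. When a 24:16 split favours BNS, unadjusted false non-inferiority is roughly 8% to 14% over the assumed order effects. With no order effect it is 5%. These figures depend on reading 0.24 SD as a fixed margin, which 17.1 leaves open.

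Two further inferences go too far. One is that a 20:20 split alone settles the matter: it removes the mean shift but not the loss of power in step 7, so the order term is needed as well. The other is that a particular level or side is confounded with drug. Within a patient the first drug goes to the first site, but the protocol does not say which anatomical site that is, and balancing sequences does not by itself balance anatomy.

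**What to change.** 1. **Section 17.3, with a matching phrase in 6.2.** Replace the wording on arms with: each participant is randomised 1:1 to one of two sequences, BNS then lidocaine or lidocaine then BNS, in concealed permuted blocks of varying size, 20 participants per sequence. Because 14.2 does not count aborted procedures towards the 40, add that they are replaced within the same sequence.
2. **Section 17.1.** Require the sequence (injection-order) term in the analyses of both hypotheses, including the ordinal fallback for Hypothesis 1, and take the Hypothesis 2 confidence limit from the adjusted model.
3. **Sections 6.2 and 6.5.** State that the first and second sites are fixed before the first syringe is taken up, and record level and side for each wheal, so that score, site and sequence can be linked.

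The cost is a few sentences and a blocked list. N stays 40, with power of about 0.81 at effect size 0.46. The order term uses one degree of freedom. Blocking makes allocation slightly more predictable, which matters because 17.3 gives the investigators access to the envelope folder. Varying block sizes limit this, as does keeping the list with the pharmacy, which already handles blinding under 5.2.

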18.0 Provisions to Monitor the Data to Ensure the Safety of Participants*

18.1 Due to the nature of the study using products that are currently commercially available and FDA approved for injection, it is unlikely that there would be major untoward events that are novel. The most likely possible event would be an unexpected allergic reaction to either lidocaine 1% or bacteriostatic saline, which would be identified at the time of the procedure. The secondary safety data being reviewed would be patient's ability to tolerate injection of or needle insertion with both the lidocaine 1% and bacteriostatic saline. During the study, the safety data will be monitored by the fellow on rotation at Grady along with [name] (PI). The fellow on rotation will monitor safety data via case report forms completed on each procedure detailing the procedure and any complications. Safety data collection will be a continuous process via case report forms starting at the beginning of data collection. Safety data will be reviewed on a monthly basis by the fellow on their Grady rotation. If either a high rate of unexpected allergic reactions or inability of patients to tolerate injection of or needle insertion with both the lidocaine 1% and bacteriostatic saline is identified then this would trigger suspension of the research. Efficacy data will be reviewed on a quarterly basis by the six fellows and [name] (PI).

19.0 Provisions to Protect the Privacy Interests of Participants

19.1 Patients will only be interacting with providers who would otherwise be participating in their care regardless of participation in the study. Participation in the study will not introduce any additional persons interacting with the patients.

19.2 The questions being asked will be standardized and will only be evaluating a patient's level of pain during an examination or procedure they would otherwise be receiving regardless of their participation in the study. No additional examinations or procedures will be asked of the patient's that they would not otherwise receive due to their diagnosis or plan of care.

19.3 The research team, consisting of the current pain fellows and [name] (PI), will access patient information via the Epic EEMR system at Grady Memorial Hospital. No information other than that would otherwise be available in order to routinely treat patients will be made available.

20.0 Economic Burden to Participants

20.1 Participants will not incur any costs related to participation in this study.

21.0 Consent Process

21.1 Consent will be obtained from participants in person the day of the procedure. This will be performed in an exam room prior to taking the patient to the procedure room. Consent will be obtained by an investigator. All researchers will be educated on the patients and procedure that this study is applicable towards in order to ensure the consistent consenting process of applicable patients. No waiver for any elements of the consent or HIPAA authorization will be needed. The therapeutic/diagnostic procedure performed on the patient will be unchanged, only the solution injected for skin topicalization will be randomized therefore no changes to the procedure consent form must be made. No vulnerable groups (children, prisoners, pregnant women, cognitive impairment, and employees) will be included in the study. The risk of coercion or undue influence in enrolling patients in this study is low. However all individuals obtaining consent will be educated on ethical practice and the voluntary nature of patient participation in this research study. Comprehension of the informed consent will be ensured by providing both verbal and written detailed information to the patient. The patient will also be asked if they have any questions, and if so ample time will be allowed for clarification.

Non-English-Speaking Participants N/A N/A

Participants who are not yet adults (infants, children, teenagers) N/A N/A

Cognitively Impaired Adults N/A N/A

Adults Unable to Consent N/A N/A

22.0 Process to Document Consent in Writing

22.1 Consent will be documented in writing by having the participant sign the consent document. A copy will be provided to the participant and the original document will be stored in a locked cabinet in a locked office in the clinic.

22.2 Consent document attached.

23.0 Setting

23.1 The research study will be conducted at the Grady Pain Clinic which is located on the first floor of Grady Memorial Hospital in area 1A. Identification, screening, consent, and procedures will all be conducted in this clinic.

24.0 Resources Available

PROTOCOL TITLE: Bacteriostatic Normal Saline versus lidocaine for intradermal anesthesia during lumbar medial branch block.

24.1 The Grady Pain Clinic is located on the first floor (1A) of Grady Memorial Hospital. It has 4 exam rooms, 1 procedure/fluoroscopy room, and 1 recovery room. There is one LPN at this time with positions for one RN and one CMA outstanding. The clinic sees over 300 patients a month with the majority of those patients having chronic low back pain. A lumbar medial branch block is a diagnostic/prognostic procedure performed to identify back pain from lumbar facet joints and likely response to radiofrequency ablation of the medial branch nerves. From examining past procedure volume, this procedure is performed three to four (3-4) times a week on average. We anticipate fifty (50) potential participants over the four (4) months window and expect enrollment of 80% or forty (40) participants.

24.2 This research is being performed as part of the Pain Medicine Fellowship research/quality improvement project. The principal investigator, [name], MD, is Director of the Grady Pain Clinic and works full-time at the clinic. Pain Medicine fellows rotate through the clinic on a monthly basis and will participate in research study as co-investigators. We anticipate an additional thirty (30) minutes to complete the screening, consent, and study intervention. The principal investigator will devote four to five (4-5) hours per week to conducting and completing the research.

24.3 The nursing staff will be informed about the protocol prior to initiating enrollment; however, nursing staff will not be directly involved in aspects of the research, just the investigators. The co-investigators meet on a monthly basis currently and will continue until the study is completed.

24.4 As mentioned earlier, the risk of pain/discomfort with this research study will be short-lived. In the event of an allergic reaction, although unlikely, the patient will be managed supportively in the Pain Clinic similarly to any other patient that may experience an allergic reaction during a procedure and will be referred to the Grady's Allergy clinic. If the patient reports psychological issues related to their participation in this study, the patient will be referred to Grady's mental health department at [name].

